### 5.2.4 Baseline Values

Baseline values that are missing will not be imputed for safety or efficacy measures. For efficacy assessments scheduled to be collected at more than one visit during the Screening/Baseline period, the baseline value will be based on the average of all nonmissing values from assessments conducted prior to the first dose of study drug. For assessments scheduled to be collected once during the Screening/Baseline period, the value from the most recent non-missing assessment prior to the first dose will be used. For safety and other assessments, the value from the most recent non-missing assessment prior to the first dose will be used.

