### 5.2.5 Post-Baseline Values

For subjects who discontinue the study, data will be analyzed up to the last observation for safety and efficacy measures. Missing data for safety assessments will not be imputed. For efficacy rating scale measures other than the exceptions listed below, if an assessment has been completed but has missing items, missing values shall be imputed as follows:

- If 3 or fewer items are missing, the last observation for that particular data element (e.g., item response) will be carried forward.
- The scoring algorithms will be applied including the observed values and last observation carried forward (LOCF) for the missing items

These rules will only apply to individual items. Total scores, subdomain and subscale scores will not be carried forward. If the assessment is completely missing, items will not be imputed.

These imputation rules do not apply to the CGI-I, Clinical Global Impression Scale – Severity (CGI-S) or Caregiver Impression of Change assessments. If a particular domain is missing for these assessments, the participant will be excluded from the corresponding analysis. These imputation rules also do not apply to the Caregiver Top 3 Concerns assessment. If a concern is missing for this assessment, the average severity will still be calculated from all non-missing concern severity scores.

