- Attention Deficit Disorder will be derived from the PTHS diagnosis page of the CRF. If "Attention Deficit Disorder" is checked under "confirmation of psychiatric co-morbidities", the subject is considered as having the disorder.
- Obsessive-compulsive Disorder will be derived from PTHS diagnosis page of the CRF. If "Obsessive-compulsive disorder" is checked under "confirmation of psychiatric co-morbidities", the subject is considered as having the disorder.
- There will be three age group definitions use for the analysis and applied to all analyses requiring an analysis by age group:
  - Enrollment Age Group
    - 13 to 17 years old
    - 8 to 12 years old
    - 3 to 7 years old
  - Child/Adolescent Age Group
    - 13 to 17 years old
    - 3 to 12 years old
  - Divided Age Group
    - 16 to 17 years old
    - 13 to 15 years old
    - 8 to 12 years old
    - 3 to 7 years old
- Dose modification is defined as dose increased, dose reduced, or dose interrupted responses for the action taken with study treatment on the AE CRF.
- TEAEs are defined as those adverse events that occurred after the administration of first dose of study drug.
- Improvement in the Top 3 concerns will be derived as a decrease in severity (change from baseline < 0). This is calculated for the average score and for individual concerns by the symptom domains as defined in Section 9.2.8.

- The baseline seizure frequency will be determined based on the number of seizures recorded in the diary during the 4–6-week screening period. The baseline monthly seizure frequency will be derived by dividing the total number of seizures during the screening/baseline period by the screening/baseline duration in months (screening/baseline duration divided by 30.4375). During the treatment period (Visits 4 6), the seizure frequency will be derived by summing the number of seizures recorded in the diary over treatment. The monthly seizure frequency will be derived by dividing the total number of seizures during the treatment duration in months (screening/baseline duration divided by 30.4375).

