### 9.2.8 Caregiver Top 3 Concerns Rating

The Caregiver Top 3 Concerns Rating assessment will be completed at all Screening/Baseline period visits (Visits 1, 2, 3), as well as Week 6 (Visit 9), End of Treatment (Week 13, Visit 16), and Follow-up (Visit 17). The three concerns identified at Screening/Baseline are carried forward and rated at the follow-up visits.

Caregivers are asked to identify 3 concerns from among 11 clinically important symptom domains: Language/Communication, Social interest/Avoidance, Repetitive Behaviors, Challenging Behaviors, Gross motor skills, Fine motor skills, Gastrointestinal problems, Breathing Disruptions, Sleep, Seizures, and Self-care skills. Each individual concern identified should be from a different symptom domain, but caregivers can select any domain and choose any symptom of concern within that domain.

The severity of each concern is scored using a 10-point Likert scale of severity. Average Top 3 concern severity is defined as the average of severity scores for the three concerns. Lower scores indicate lesser severity. The average score (i.e., average of the severity scores for the Top 3 concerns) will have a range of 0 to 10. Improvement in concern average severity is defined as a change from baseline score < 0.

If the caregiver does not list the same 3 concerns on the Top 3 Concerns Follow-Up CRF that were recorded on the Top 3 Concerns Screening CRF (completed at Visit 1), then their responses will be reviewed and may not be included in analysis. A review of all concerns will be done prior to database lock, and visits with incorrect concerns will be flagged as unusable for analysis.

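### When a Top 3 concern is unrated at follow-up, change in average severity compares two concerns with three and is not zero even in an unchanged child

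*SAP*

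**What the plan says.** SAP 9.2.8 has each caregiver name three concerns and rate their severity at Visits 1, 2 and 3, Week 6, EOT and Follow-up. On their choice it says: "Each individual concern identified should be from a different symptom domain". On the scale: "The severity of each concern is scored using a 10-point Likert scale of severity". On the summary score: "Average Top 3 concern severity is defined as the average of severity scores for the three concerns".

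SAP 5.2.5 fills in missing items on most rating scales by carrying the last item response forward. It then adds: "These imputation rules also do not apply to the Caregiver Top 3 Concerns assessment". Instead, when a concern is missing, "the average severity will still be calculated from all non-missing concern severity scores".

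For efficacy measures scheduled more than once before dosing, SAP 5.2.4 says "the baseline value will be based on the average of all nonmissing values from assessments conducted prior to the first dose of study drug". SAP 5.3 defines change as the visit value minus the baseline value. SAP 5.3 and 9.2.8 both count any change below zero as improvement, with no minimum size.

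Under 9.2.8 the change in average severity is tested with a Wilcoxon signed rank test at Week 6 and EOT, plotted, and turned into a count of improved children. The same section describes a review before database lock of follow-up forms that do not list the original three concerns, after which "visits with incorrect concerns will be flagged as unusable for analysis".

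The sections that the SAP addendum lists as updated do not include 5.2.4, 5.2.5 or 9.2.8.

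**The concern.** The three concerns are not interchangeable items of one scale. They are chosen for the individual child from different domains; one child's set might be seizures, sleep and fine motor skills. Their severities can differ widely. If one is unrated at a visit, the visit average covers two symptoms and the baseline average covers three. Part of the difference then reflects which concern dropped out, not what happened to the child.

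No passage restricts the baseline to the concerns rated at the visit, and none sets a minimum number of rated concerns. Section 9.2.8 defines the score over three concerns while 5.2.5 allows fewer, so the two sections also do not agree on what the score is.

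At stake are the Wilcoxon test on the average, its plots and the improvement count. The count is sensitive because any value below zero qualifies.

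**Working it through.** The plan gives no figure for this measure to reproduce. The check is algebra on the SAP's own rules, followed by an assumed range for size.

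**The artefact.** Let S be the sum of the three baseline severities and x the baseline severity of the concern missing at follow-up. Suppose the child has not changed.

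- Visit average (5.2.5): (S − x)/2
- Baseline average (5.2.4): S/3
- Change (5.3): (S − x)/2 − S/3 = (S − 3x)/6 = (S/3 − x)/2

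So the change is half the gap between the baseline mean and the missing concern. It is zero only when the missing concern equals that mean.

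**Unchanged children, one concern missing**

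| Baseline | Missing | Visit average | Baseline average | Change | Classed as |
|---|---|---|---|---|---|
| 9, 6, 3 | 9 | 4.5 | 6.0 | −1.5 | improved |
| 9, 6, 3 | 3 | 7.5 | 6.0 | +1.5 | not improved |
| 8, 7, 6 | 8 | 6.5 | 7.0 | −0.5 | improved |

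**Changed children, baseline 9, 5, 4 (average 6.0)**

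- True worsening to 10, 5, 5: fully rated, 6.67 − 6.0 = +0.67. With the 10 missing, 5.0 − 6.0 = −1.0, classed as improved.
- True improvement to 8, 4, 3: fully rated, 5.0 − 6.0 = −1.0. With the 3 missing, 6.0 − 6.0 = 0, not improved.

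**Size among children with one concern missing.** The documents give no spread of severities within a child, so a range is assumed: integer scores 1 to 10, centred at 6, no true change, no rating noise, the missing concern chosen at random (simulation, 400,000 children per row).

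| Within-child SD (assumed) | SD of artefact | Artefact of 1 point or more, either direction |
|---|---|---|
| 1 | 0.4 | 3% |
| 2 | 0.8 | 26% |
| 3 | 1.1 | 42% |

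At SD 2, about 46% fall below zero and about 46% above. Enumerating every baseline triple on a 1 to 10 scale as equally likely gives 47.5% below, 47.5% above and 5% at zero. The error is symmetric when missingness is unrelated to severity.

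**With rating noise.** Real ratings vary from visit to visit. Adding assumed noise of SD 0.5 or 1 per rating, with within-child SD 2 and a three-visit baseline, about 43% to 47% of unchanged, fully rated children already fall below zero. With one concern missing the figure is about 49%.

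**Effect of one child.** 1/20 = 5 percentage points; 1/10 = 10 percentage points.

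**After matching.** Restricting the baseline to the concerns rated at the visit:

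- Unchanged 9, 6, 3 with the 9 missing: 4.5 − 4.5 = 0.
- Worsening 9, 5, 4 to 10, 5, 5 with the 10 missing: 5.0 − 4.5 = +0.5, no longer improved.
- Improvement 9, 5, 4 to 8, 4, 3 with the 3 missing: 6.0 − 7.0 = −1.0, improved.

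**The case against.** The case for leaving this alone has real content.

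- **It may be rare.** The form has three ratings. The protocol has the Investigator review caregiver assessments at Week 6 and EOT (9.2.9, 9.2.16) and requires omissions on the eCRF to be explained (13.2). This stands as a reason to expect few cases, but it does not say how to score those that occur.
- **A matched analysis exists.** Change and improvement by symptom domain are planned in 9.2.8, and each concern is there compared with itself. This stands and limits the point to the average score.
- **The pre-lock review is a safeguard.** It is one for visits that list the wrong concerns, and read plainly it removes the visit. It does not clearly reach a correctly listed concern left unrated.
- **The stakes are modest.** The measure is one of many secondary efficacy measures, there is no primary efficacy variable (8.1), and tests are descriptive (5). This stands.

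Two stronger readings are tempting. A reader might infer that the rule favours the drug, because losing the worst concern produces improvement. Nothing in the documents suggests that the worst concern is likelier to be missing, and losing the mildest one has the opposite effect. A reader might also take the 46% to mean that nearly half of unchanged children are false improvers because of this rule. That figure applies only to children with one concern missing and assumes noise-free ratings. With noise, the cutoff at zero already classes a similar share of fully rated unchanged children as improved, and the missing-concern rule adds about two to six percentage points among affected children.

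**Conclusion.** The point holds as a scoring defect. As written, SAP 5.2.4, 5.2.5 and 5.3 together give a child with one unrated concern a change that includes (baseline mean of three − missing concern)/2, whatever the child's course. The algebra needs no assumption beyond the SAP's rules. The size does: over an assumed within-child SD of 1 to 3 points, the artefact has SD about 0.4 to 1.1 among affected children.

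The consequence is noise and misclassification in the average, its test, its plots and its improvement count. Bias in the average would require missingness to depend on severity, which the documents neither state nor exclude. Without a rate of missing concerns, no study-level effect can be given. The small sample is the reason it still deserves correction: a single misclassified child is visible in the reported rate.

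**What to change.** In SAP 5.2.5 and 9.2.8, define change in average severity as the mean of the within-concern changes over concerns rated both before dosing and at that visit. Equivalently, recompute the baseline average over the concerns rated at that visit, taking each concern's baseline as the mean of its own non-missing pre-dose ratings. Use this change for the Wilcoxon test, the plots and the improvement count, and make the 9.2.8 definition of the average agree with it.

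This keeps every partly rated child and returns exactly zero when the rated concerns have not moved. It cannot say what happened to the unrated concern, so report how many children had fewer than three concerns rated at each visit. Requiring all three concerns would also remove the artefact, but at the price of dropping partly rated children from a small sample. The cutoff at zero is a separate matter that this change leaves as it is.

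The cost is one SAP sentence and a small programming change, with no new data.

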### 5.3 Definitions

- Age will be derived as the integer value of (informed consent/assent date date of birth + 1)/365.25.
- The age at time of assessment will be derived as the integer value of (date of assessment date of birth + 1)/365.25.

- Body Mass Index (BMI) will be derived as weight in kilograms divided by height in meters squared.
- The change from Baseline measurement for a variable at a particular visit will be derived as the measurement taken at the specified visit minus the baseline measurement. For the Clinical Global Impression Scale Improvement and Caregiver Impression of Change, change from Baseline is the value at the visit.
- Treatment duration in days will be derived as follows: Date of Last Dose Date of First Dose + 1.
- The number of expected doses will be derived as (2\*treatment duration in days)-1, as subjects are expected to receive only their morning dose on the last day of treatment
- The number of doses taken will be derived as the number of doses taken as indicated by the Administration of First Dose CRF and by the Daily Dosing Log CRF for remaining doses, based on completed date and dose fields
- Number of missed doses will be derived based on the number of expected doses the number of doses taken
- Study Day will be derived as Date of Event Date of First Dose (+1 if the date of event ≥ date of first dose)
- Screening/baseline duration in days will be derived as follows: Date of First Dose Date of Screening
- Study duration will be defined as the total number of days in the study (date of last visit date of informed consent + 1).
- History of developmental regression will be determined from the PTHS diagnosis page of the CRF question: "Has the child undergone a regression of skills in the past?" If coded as "yes" the subject is considered as having had a past developmental regression.
- Autism Spectrum Disorder (ASD) diagnosis will be derived from the PTHS diagnosis page of the CRF. If ASD is checked under "confirmation of psychiatric co-morbidities", the subject is considered as having the disorder.
- Bipolar Disorder will be derived from the PTHS diagnosis page of the CRF. If "Bipolar disorders" is checked under "confirmation of psychiatric comorbidities", the subject is considered as having the disorder.

- Attention Deficit Disorder will be derived from the PTHS diagnosis page of the CRF. If "Attention Deficit Disorder" is checked under "confirmation of psychiatric co-morbidities", the subject is considered as having the disorder.
- Obsessive-compulsive Disorder will be derived from PTHS diagnosis page of the CRF. If "Obsessive-compulsive disorder" is checked under "confirmation of psychiatric co-morbidities", the subject is considered as having the disorder.
- There will be three age group definitions use for the analysis and applied to all analyses requiring an analysis by age group:
  - Enrollment Age Group
    - 13 to 17 years old
    - 8 to 12 years old
    - 3 to 7 years old
  - Child/Adolescent Age Group
    - 13 to 17 years old
    - 3 to 12 years old
  - Divided Age Group
    - 16 to 17 years old
    - 13 to 15 years old
    - 8 to 12 years old
    - 3 to 7 years old
- Dose modification is defined as dose increased, dose reduced, or dose interrupted responses for the action taken with study treatment on the AE CRF.
- TEAEs are defined as those adverse events that occurred after the administration of first dose of study drug.
- Improvement in the Top 3 concerns will be derived as a decrease in severity (change from baseline < 0). This is calculated for the average score and for individual concerns by the symptom domains as defined in Section 9.2.8.

- The baseline seizure frequency will be determined based on the number of seizures recorded in the diary during the 4–6-week screening period. The baseline monthly seizure frequency will be derived by dividing the total number of seizures during the screening/baseline period by the screening/baseline duration in months (screening/baseline duration divided by 30.4375). During the treatment period (Visits 4 6), the seizure frequency will be derived by summing the number of seizures recorded in the diary over treatment. The monthly seizure frequency will be derived by dividing the total number of seizures during the treatment duration in months (screening/baseline duration divided by 30.4375).

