11.3 Efficacy Analysis

Efficacy will be assessed by looking at within-participant changes from the Baseline period to the EOT using the efficacy endpoints listed in Section 6.3.2.

The participant's baseline characteristics and symptom severity will be established based on assessments collected during the 4 to 6 week Screening/Baseline period. Baseline values will be based on the average values of visits 1, 2, and 3 for assessments collected at more than one visit. A Wilcoxon signed rank test will be used to test for improvement and an exact significance level will be computed.

Potentially influential factors will be considered and addressed with a linear regression model. This model may include covariates such as age, sex, nonverbal NVIQ or NVIQ equivalent, genotype, history of regression (yes/no), ASD diagnosis (yes/no) with no more than two covariates included in any model. Descriptive statistics and corresponding graphics will be used to present the results. The safety and efficacy analysis details will be specified in the SAP.

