### 5.1 Determination of Sample Size

Sample sizes were estimated for this open-label study using within-subject change as the measure of improvement. Given the limited data from interventional trials in these patient populations and that this is the first clinical study of NNZ-2591 IMP in this population, treatment change estimates were based on Clinical Global Impression Scale of Improvement (CGI-I) data from completed clinical trials in other rare, neurodevelopmental disorders. Based on the information provided in Glaze et al. 2019 (Double-blind, randomized, placebo-controlled study of trofinetide in pediatric Rett syndrome), the standard deviation of the CGI-I is approximately 0.7 at a single timepoint. For a sample size of 10 subjects, a two-sided significance level of 0.05, and a Wilcoxon signed-rank test, the study will be able to detect a difference of 0.87 units of change in the CGI-I at a power of 0.90. For a power of 0.80, 0.85, and 0.90, the detectable difference would be 0.75, 0.80, and 0.87 or larger, respectively. The effect size for a power of 0.80, 0.85, and 0.90 is 1.07, 1.14, and 1.24, respectively. If the observed standard deviation is 1.5, the detectable difference for a power of 0.80, 0.85, and

0.90 is 1.61, 1.71, and 1.86 or larger, respectively. For a sample size of 20 subjects, a two-sided significance level of 0.05, and a Wilcoxon signed-rank test, the study will be able to detect a difference of 0.55 units of change in the CGI-I at a power of 0.90. For a power of 0.80, 0.85, and 0.90, the detectable difference would be 0.48, 0.51, and 0.55 or larger, respectively.

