#### 9.2 Secondary Efficacy Analysis

The efficacy endpoints will be analyzed using a Wilcoxon signed rank test on the paired subject data from baseline to end of treatment (Visit 16) and Visit 9 (Week 6) when applicable. Descriptive statistics will be used to summarize the data. For total scores (and certain subscale score as defined below) waterfall plots and histograms or bar charts (as appropriate) will also be created at the End of Treatment (EOT) visit with plots for all subjects and separate plots indicating each of the following: age groups, NVIQ/DQ score (>= 50, < 50), sex (Male, Female) and number of concomitant medications  $(> 6, \le 6)$ . The number of concomitant medications will be determined as defined in Section 5.3. Line graphs plotting scores by visit will also be generated for the mean group data and showing individual participants. The NVIO/DO score is the SB5 Non-Verbal Intelligence Quotient (z-deviation), or the BSID-4 Non-verbal Developmental Quotient depending on which assessment the subject took. The number and percentage of subjects who had an IQ/DQ score  $\geq 50$  and < 50 at Baseline and End of Treatment will be presented in a table for NVIQ/DQ, VIQ/DQ, and FSIQ/Overall DQ. For assessments that use discrete scores, the histograms will be changed to bar charts. If the change from baseline of the discrete scores is presented, then the change from baseline value will be rounded using conventional rounding standards for ease of presentation and understanding in the bar chart. For scales with domain scores, forest plots displaying the mean change from baseline and 95% CI for each domain score at EOT will be generated. All figures will be generated on the ITT and mITT populations.

Exploratory analyses on some endpoints using linear regression may be performed to assess the relationship between treatment and specified covariates or combinations of covariates. The empirical cumulative distribution function will be plotted for certain variables. As appropriate, collective response analysis may be done to assess data across subjects.

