#### 9.2.1 Clinical Global Impression Scale - Overall Improvement Score

CGI-I assessments are completed at Visit 9 (Week 6), End of Treatment (Week 13, Visit 16), and Follow-up (Visit 17). The clinician rates how much the subject's illness has improved or worsened relative to Visit 3 (Week 0). The Overall CGI-I score is rated on a 7-point scale, where 1='very much improved'; 2='much improved'; 3='minimally improved'; 4='no change'; 5='minimally worse'; 6='much worse'; 7='very much worse'. Scores of 1, 2, and 3 indicate improvement. Within subject change is indicated by the score at each relevant follow-up visit (Week 6, Visit 9 and Week 13, EOT, Visit 16). If an overall score is missing, that subject will be excluded from analysis at that visit.

Summary statistics for the CGI-I Overall score will be displayed at all post-baseline visits. Within subject changes will be analyzed using a Wilcoxon signed rank test at EOT and Week 6. The overall score will be presented in figures as described in Section 9.2. As this score is categorical, the waterfall plots will be adjusted so a score of "7 – Very Much Worse" will be presented at the bottom of the graph and a score of "1 – Very Much Improved" will be presented at the top of the graph. The overall score will also be presented as a line graph at post-baseline visits.

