### 9.2.4 Clinical Global Impression Scale - Severity - Overall Severity Score

Clinical Global Impression of Severity assessments will be made at the Screening visit (Visit 1), Visit 3 (Week 0), Visit 9 (Week 6), End of Treatment (Week 13, Visit 16), and Follow-up (Week 15, Visit 17). The overall severity score is scored on a 7-point scale, where 1='typical for age, not at all impaired'; 2='borderline, slightly impaired'; 3='mildly impaired'; 4='moderately impaired'; 5='markedly impaired'; 6='severely impaired'; 7='among the most severely impaired'. Lower scores reflect less impairment. Within subject change is the difference between the score at each relevant follow-up visit and the score at baseline. If a score is missing, the subject will be excluded from the corresponding summaries.

The overall score and change from baseline at each post-baseline visit will be summarized using descriptive statistics. Within subject changes will be analyzed using a Wilcoxon signed rank test at Week 6 and EOT. Test-retest reliability will be assessed for all scores collected during the Screening period (Visits 1 and 3) using ICC. The change from baseline in the overall score at EOT will be presented in figures as described in Section 9.2. The overall score will also be presented as a line graph at post-baseline visits.

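### SAP 9.2.1 tests the raw 1–7 CGI-I score with a signed-rank test but states no null value; against zero, the p-value cannot tell improvement from worsening

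*SAP*

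**What the plan says.** SAP 5.3 defines change from baseline in general as the visit measurement minus the baseline measurement, and then makes an exception: "For the Clinical Global Impression Scale Improvement and Caregiver Impression of Change, change from Baseline is the value at the visit".

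SAP 9.2.1 repeats this for the CGI-I overall score: "Within subject change is indicated by the score at each relevant follow-up visit". It labels 4 as no change, calls scores of 1 to 3 improvement, and sets the test: "Within subject changes will be analyzed using a Wilcoxon signed rank test at EOT and Week 6". No reference value follows.

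The general rule in SAP 9.2 does not supply one: "The efficacy endpoints will be analyzed using a Wilcoxon signed rank test on the paired subject data from baseline to end of treatment". CGI-I is first rated at Week 6, so it has no baseline score to pair with.

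Protocol 11.3 gives the purpose of the test: "A Wilcoxon signed rank test will be used to test for improvement and an exact significance level will be computed".

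The addendum reopens 5.3 only for the count of missed doses and does not revise 9.2.1.

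**The concern.** A signed-rank test needs a value to test against. For a variable called change, the usual value is zero. That is right for the CGI-S in SAP 9.2.4, where change is a true difference and the instruction is almost word for word the same: "Within subject changes will be analyzed using a Wilcoxon signed rank test at Week 6 and EOT". It is wrong for the CGI-I as 5.3 defines it, because a child with no change scores 4 and no child can score zero or below.

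Section 9.2.1 adapts the display to the CGI-I coding ("As this score is categorical, the waterfall plots will be adjusted so a score of" 7 appears at the bottom), but it does not adapt the test.

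At stake is the p-value of the endpoint used for sizing. Against zero it would be small whether the children improved, stayed the same or got worse, so it could not serve the purpose in protocol 11.3. Independent programming (SAP 5) may not expose this if both programmers work from the same text.

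**Working it through.** **Inputs.** Scale 1 to 7 with 4 as no change (SAP 9.2.1); two-sided alpha 0.05, SD about 0.7, n = 10 and n = 20 (SAP 5.1); exact significance level (protocol 11.3; the SAP does not say). The score sets and the simulation model below are illustrative assumptions with an SD near 0.7.

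**1. The plan's own figure.** SAP 5.1 says "the study will be able to detect a difference of 0.87 units of change in the CGI-I at a power of 0.90" with 10 subjects. Noncentral-t power with effective sample size floor(n × 3/π) reproduces the figures:
- n = 10 gives floor(9.55) = 9 and effect sizes 1.067, 1.142 and 1.238 at power 0.80, 0.85 and 0.90. Times 0.7, these are 0.747, 0.800 and 0.866 (stated: 0.75, 0.80, 0.87).
- n = 20 gives floor(19.10) = 19 and differences 0.476, 0.509 and 0.551 (stated: 0.48, 0.51, 0.55).

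The sizing is sound as a distance from no change. It cannot be a distance from zero: a child with no change would already be 4/0.7 = 5.7 SDs away.

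**2. Exact test against zero.** Every score is at least 1, so every signed rank is positive and the statistic takes its extreme value. Two-sided p = 2/2^n:
- n = 6: 2/64 = 0.031
- n = 10: 2/1,024 = 0.00195
- n = 20: 2/1,048,576 = 0.0000019

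Ten scores of 1, ten of 4 and ten of 7 all give 0.00195.

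**3. Normal approximation against zero** (tie-adjusted variance, no continuity correction). Here z = [n(n+1)/4]/√V, with V = n(n+1)(2n+1)/24 − Σ(t³ − t)/48, where t is the size of each group of tied scores. The scores enter only through the tie pattern. Over every possible set of scores:

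| n | sets | smallest p | largest p |
|---|---|---|---|
| 6 | 924 | 0.0143 | 0.0277 |
| 10 | 8,008 | 0.0016 | 0.0050 |
| 20 | 230,230 | 0.0000077 | 0.000085 |

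All are below 0.05.

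**4. Three sets of ten scores, null 0 versus null 4.**

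| Set | mean | approx. p vs 0 | exact p vs 4 |
|---|---|---|---|
| No net change: 3,3,4,4,4,4,4,4,5,5 | 4.0 | 0.0041 | 1.00 |
| Improved: 2,2,3,3,3,3,3,4,4,4 | 3.1 | 0.0044 | 0.0156 |
| Worsened (mirror image): 6,6,5,5,5,5,5,4,4,4 | 4.9 | 0.0044 | 0.0156 |

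For the improved set against zero, the tie groups are 2, 5 and 3. So V = 96.25 − (6 + 120 + 24)/48 = 93.125, z = 27.5/9.65 = 2.85 and p = 0.0044. Against 4, three differences are zero and the other seven share one sign, so p = 2/2⁷ = 0.0156. The two-sided p against 4 is the same for the worsened set, but there the sign of the statistic shows the direction. Against zero the sign is positive for all three sets.

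**5. Simulated no-change group** (normal, mean 4, SD 0.7, rounded and clipped to 1–7; 10,000 trials; exact test at 0.05). Against zero, 100% are declared significant at n = 10 and at n = 20. Against 4 the rates are 0.7% and 2.2%, below 5% because of ties and zeros. A separate run of 5,000 trials gave 100% against zero, and 0.6% and 1.9% against 4.

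**The case against.** The strongest reply is that the SAP never prescribes a null of zero. The labels make 4 the only sensible reference, and zero lies off the scale, so the figures against zero measure a programming error that may never occur. This stands in part: the harm is conditional. But the literal definition in 5.3, joined to the test in 9.2.1, leads to zero, and nothing in the text stops it.

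SAP 5 also provides for lead-statistician review and for validation that the methods are statistically sound, and the list of tables is kept outside the SAP. Either might catch the point or settle it. Neither puts the null value in the plan.

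The consequence is modest, and that stands fully. There is no primary efficacy variable, SAP 5 calls the tests descriptive, and SAP 8.5 plans no formal analysis. A tiny p-value beside a mean near or above 4 would look wrong to a careful reader.

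Two smaller points also stand. The inference to 4 rests on the labels more than on the sizing: 0.87 is below the scale minimum of 1, but the differences given for an SD of 1.5 (1.61 to 1.86) are not. And the SAP governs where it conflicts with the protocol, so the phrase in protocol 11.3 does not by itself repair the SAP.

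**Conclusion.** The concern holds. The test in SAP 9.2.1 has no stated null value, and the variable it is applied to is coded so that the customary null of zero gives a meaningless p-value. If zero is used, every analysis of six or more subjects is significant at 0.05 whatever the scores, by the exact test or by the normal approximation. If 4 is used, the illustrative no-net-change set gives p = 1.00 and the improved set 0.0156.

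The figures against zero are a conditional worst case, not a description of what the plan orders. The results in step 2 and the ranges in step 3 of the check hold for any scores; the three example sets and the simulation rest on the assumptions stated there. The 5.3 convention is acceptable for summaries and plots, and the sample-size figures are unaffected. This should be fixed, but it does not threaten the primary safety and pharmacokinetic objective.

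**What to change.** In SAP 9.2.1, state that the signed-rank test is applied to the CGI-I score minus 4 (null hypothesis: median score 4; negative values mean improvement). Keep the 1–7 score and the 5.3 convention for summaries and plots.

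Three minor clarifications could be made at the same time:
- **9.2.2:** it says only that domain scores are summarized like the overall score. State whether they are tested and, if so, use the same rule.
- **9.2.3:** it names no test for the Caregiver Impression of Change. State whether the general rule in 9.2 applies and, if so, use a null of 4, the unchanged category.
- **Exact p-value:** state in the SAP whether it is exact, as in protocol 11.3.

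The cost is one clause in 9.2.1, a null value of 4 in the test program, and a sentence for each clarification adopted. No new data are needed, and the displays and sample-size figures do not change.
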